1. AMENDMENT HISTORY

Amendment No.	CIP Version No.	Date Issued	Author(s) of Changes	Details of Changes

2. LIST OF APPENDICES

Appendix A	List of intra-operative complications
Appendix B	List of device issues not leading to (S)AE
Appendix C	Case Report Form (S)AEs reporting
Appendix D	Device deficiency Form
Appendix E	Informed Consent Form

3. ABBREVIATIONS

AE	Adverse Event
AR	Adverse Reaction
BCVA	best-corrected visual acuity
CA	Competent Authorities
CIP	Clinical Investigation Plan
CRA	Clinical Research Associate
CRF	Case Report Form
EC	Ethics Committee (see REC)
EMR	Electronical Medical Record
GCP	Good Clinical Practice
GP	General Practitioner
IB	Investigator Brochure
ICF	Informed Consent Form
ICH	International Conference of Harmonization
IRB	Independent Review Board
Log MAR	logarithm of the minimal angle of resolution
PI	Principle Investigator
SAE	Serious Adverse Event
SAR	Serious Adverse Reaction
SUSAR	Suspected Unexpected Serious Adverse Reactions

4. CLINICAL INVESTIGATION SUMMARY

Title	EVA Nexus Field Observation Study
Reference Number (Acronym)	EVA Nexus
Clinical Phase	Non applicable
Objectives	To perform a field observation study using the newly developed EVA Nexus vitrectomy device.
Endpoints	Primary endpoint: determine the safety and effectiveness of the device.
Design	Investigator-initiated, mono-center, academic, prospective, observational case study
Data Collection	
Total duration of study for each patient will be 2 days (from surgery date to last follow-up day)
 
See Study Flow Chart 7.3

Planned Clinical investigation Period	Q2-Q3 2021
Clinical investigation population	
Patients that are scheduled for intra-ocular surgery regardless of the indication:
 
 • Vitrectomy surgery • Cataract surgery • Vitrectomy combined with cataract surgery
Number of Participants	Up to 250, inclusion period of three months.
Inclusion/Exclusion Criteria	
Inclusion criteria
 
 • Patients that are scheduled for intra-ocular surgery regardless of the indication: 
 • Vitrectomy surgery • Cataract surgery • Vitrectomy combined with cataract surgery • In case of (combined) vitrectomy: primary or repeat vitrectomy • General or retrobulbar anesthesia, the latter can be combined with sedation • Patients aged \geq 18 years 
Exclusion criteria
 
 • Patients aged $<$ 18 years
Device Name	EVA Nexus (CE-labeled device)
Principle Intended Use	The device is intended to be used during ophthalmic surgery.

Manufacturer Name

DORC B.V.

5. INTRODUCTION

5.1 Vitrectomy device

In certain disorders of the retina and the vitreous a vitrectomy study can be performed. For vitrectomy surgery, a surgical device is used, called "vitrectomy device". Such device integrates many functions:

1. Vitrectome driver.

A vitrectome is a small device which is inserted in the eye to remove the vitreous gel. The vitrectome has a hollow blunt-ended hollow shaft with a side opening at the distal tip. An inner hollow metal tube is moved back-and-forth over this opening, creating a guillotine-like cutting effect on the vitreous gel. At slower speeds, the vitrectome will take larger bites out the vitreous gel, hence inducing a quicker removal of the vitreous. At higher speeds, the vitrectome takes smaller bites, which is a safer approach when working close to the retina. The cutting speed is controlled by the vitrectomy machine using a foot pedal. Most of the vitrectomes are driven pneumatically, although some electrically driven versions have existed in the past.

Till about 15 years ago, the diameter of the vitrectome was 20G (1 mm), after that a switch happened to mostly 23G (0,6) and 25G (0,5) diameter instruments. Since a few years, vitrectomy instruments in 27G (0,35 mm) are available. However, this very small size has its limitations, hence is only used in less complicated surgeries.

The DORC EVA drives a pneumatic vitrectome with a maximum of 8.000 cycles per minute.

2. Aspiration system.

This is required to remove liquid from the eye. Several pump systems exist, with different ways to displace fluid:

-Vacuum pumps generate a vacuum, which is controlled by the surgeon using the foot switch of the device. The amount of fluid displacement is dependent on the amount of vacuum, and on the amount of resistance in the tubing system and instrument inside the eye. Vacuum pumps can respond quickly and can generate a large flow, but lack control to keep the fluid displacement steady when the surgeon is operating in conditions with variable resistance. An example is when working close to the vitreous base at the retinal periphery: the tip of the vitrectome will move in and out of the vitreous, resulting in high variability of the flow and risk of aspiration the retinal tissue. A typical example of a vacuum system is a venturi-pump, which is used in most of the vitrectomy devices presently available.

-Flow pumps displace a required amount of fluid, and only build up vacuum secondary to this fluid displacement. In conditions with low resistance, there is little or no vacuum-buildup. Most flow pumps are less powerful than vacuum pumps, but can provide a better control of the flow. This increases safety when working close to the retina.

A typical example of a flow pump system is a peristaltic pump. Although such pump is popular in cataract surgery, it is only used for vitrectomy surgery in conjunction with a vacuum pump.

Our present vitrectomy machine in the UZLeuven (DORC EVA) has a piston-pump which can be steered to perform as a vacuum system or as a flow system. This unique feature allows the surgeon to choose the best suitable mode for each individual step of the surgery.

3. Infusion system.

Since vitreous is removed from the eye, an infusion system must be present to maintain the eye pressure. There are two infusion systems used for vitrectomy surgery:

-Gravity system: the infusion bottle (or bag) is suspended on a telescopic infusion pole.

The pole can be extended using the vitrectomy machine to a higher or lower height, which increases the pressure at which the infusion liquid is driven towards the eye. The disadvantage of such system is that the infusion pole movement has its speed limits, which can be a problem when a fast pressure change is required in the eye (such as in case of hemorrhage).

-Air system: using a spike, air is blown into the infusion bottle. A higher air pressure will increase the force at which liquid is driving towards the eye. Such system can respond more quickly to required pressure changes. Our present vitrectomy machine in the UZLeuven (DORC EVA) has this type of infusion system.

A logistical side-effect of such air-driven system is that the infusion liquid connected to the eye must be packaged in glass bottles, since plastic bags or plastic bottles have an inherent flexibility which would cause unwanted hysteresis.

-In case of combined phaco-vitrectomy, both infusion in the anterior and in the posterior eye segment is required. Since our present vitrectomy device (DORC EVA) only has a single infusion line, the tubing needs to be reconnected from the phaco handpiece on the posterior segment infusion canula halfway the surgery.

4. Light.

A powerful light source is required to illuminate the inside of the globe during surgery. For this purpose, a PMMA fiber is connected to the light source of the vitrectomy machine and guided into the eye.

Historically, a halogen light source was used. About 15 years ago, more powerful Xenon light sources became available and are still present in many vitrectomy devices. More recently, LED light sources became more popular. Also our present vitrectomy device (DORC EVA) is equipped with an LED light source.

Increasing light output is required when using ultra-small gauge surgery (27G), since the diameter of the light fiber is extremely thin. However, care must be taken by the surgeon to avoid light toxicity when the light source is held too close to the same area of the retina for too long. Retinal damage due to light toxicity after vitrectomy can have a major effect on the visual acuity of the patient.

In most light sources for vitrectomy surgery, the light is filtered, eliminating more bluish wavelengths to increase its safety.

5. Phaco ultrasound.

To remove an opacified lens from the eye (cataract), the lens needs to be emulsified in the eye. For this purpose, a small needle is used that is oscillating on an ultrasonic frequency. These oscillations emulsify the lens material, after which can be aspirated (using the aspiration system of the device). The DORC EVA has an analog driver board and operates at a frequency of 40 kHz.

6. Laser module.

To reattach the retina in case of retinal detachment, laser coagulates need to be placed around the breaks in the retina. For this purpose, a vitrectomy machine has a built-in laser module. A glass fiber is used to guide the laser light into the eye on the retina. Using the foot switch of the device, laser coagulates can be directed towards the desired location on the retina. The DORC EVA uses a 532 nm endo laser which has been the standard for ophthalmic use.

7. Silicone oil injection.

Not infrequently, the eye needs to be filled with silicone oil during surgery for retinal detachment. For this purpose, a system is present that drives the silicone oil from a (glass) syringe into the eye. The DORC EVA can drive (pre) filled syringes of silicon oil with a pressure up to 6 bars.

8. Silicone oil extraction.

For removal of the silicone oil, a system is present that generates a high vacuum to remove the viscous oil from the eye through a small opening. The DORC EVA generates a vacuum up to 660 mmHg to remove the silicon oil.

9. Endodiathermy.

In case a hemorrhage occurs inside or outside of the eye, a diathermy probe can be connected to the vitrectomy device to coagulate the bleeding vessel. The DORC EVA operates at frequency of 1 Mhz to create the coagulation.

5.2 DORC EVA Nexus device

For the safety of the patient, the need for a performant vitrectomy device is essential. In our center, we have been using the DORC EVA vitrectomy machine since 2012. DORC will release a novel version of this surgical platform, named the EVA Nexus. This new device has several improved features compared to the present DORC EVA.

1. Vitrectome

Both EVA and EVA NEXUS provide vitrectomy. The cut speed range of EVA NEXUS, 10.000 cycles per minute, is broader than that of EVA. A higher cut speed is generally accepted as a clinical benefit, without addition of new risk.

2. Aspiration system

The aspiration system of the EVA NEXUS is the same with one additional feature. EVA NEXUS has an additional proportional controlled backflush.

The aspiration system in the DORC EVA was designed to be used with 23G/25G vitrectomy instruments. However, 27G vitrectomy is become more mainstream each year ¹⁻⁵. This feature should increase the safety during surgery when performing vitreous removal very close to the retina, also known as "vitreous base shaving".

3. Vitrectome

The maximum cut-speed of the EVA Nexus vitrectome is 20 000 cycles per minute, which is almost twice the current speed of the DORC EVA device. As explained above, this increased cut rate will also contribute to a safer removal of the vitreous close to the retina.

To maximize surgical ergonomy, the hand piece of the vitrectomy is now covered with a dampening sleeve, which reduces the amount of vibration for the surgeon holding the vitrectome during the surgery.

4. Infusion system

Our present vitrectomy device generates a desired amount of pressure in the infusion bottle (by changing the bottle height or by injection of air in the bottle), but there is no control over the actual amount of liquid that is infused in the eye. This can cause danger in two directions:

-In some circumstances, the infusion flow will be too high, which impedes normal arterial perfusion of the eye, which can create ischemic damage in the eye. Such vitrectomy-related vascular damage is not infrequently described in the literature ⁶.

-In other circumstances, the aspiration of liquid can be higher than the infusion flow, hence the eye pressure can become too low, which can cause hemorrhage or even collapse of the eye.

The EVA Nexus system has an active infusion system, which constantly provides a stable infusion to the eye and a stable intra-ocular pressure during surgery. Hence, it features automated control of the intra-ocular pressure during anterior and posterior segment surgery.

The fixed and gravity modes are both pressure controlled and can be regarded similar technology with the same functional result. The eIOP mode in EVA NEXUS supports the surgeon to maintain the IOP by maintaining the Irrigation/Aspiration balance (regulated by the pump system to get precise Intra Ocular Pressure control), where in EVA Intra Ocular Pressure is a result of the surgeon controlled settings of the system.

The EVA Nexus has twin irrigation lines, which omits the need to switch the infusion halfway the surgery in case of combined phaco-vitrectomy

Another, logistical implication is that the infusion liquid used during cataract surgery or vitrectomy surgery must not be packaged anymore in a glass bottle, since the DORC EVA Nexus actively aspirates the infusion liquid from the container. Therefore, less expensive packages of infusion liquid can be used (fluid bags or plastic bottles).

5. Light

The system had a LED-powered light source, with filtered output to eliminate the shorter light wavelengths that induce light toxicity during prolonged exposure to the retina. This is the same light source as in the present DORC EVA device.

6. Phaco ultrasound

The phaco handpiece that fits to EVA Nexus is the same CE-labeled commercial handpiece already used on our present surgical device.

Although the design is somewhat different, both EVA and EVA NEXUS use similar principles of operation to drive the phaco handpiece for emulsification or fragmentation of the lens. All performance requirements are the same.

7. Laser module

The EVA Nexus has a built-in 532 nm diode-laser. This is the same laser module as used in our present vitrectomy device.

8. Silicone oil injection (VFI).

There are no differences between the EVA and EVA NEXUS for silicone oil injection.

9. Silicone oil extraction.

There are no differences between the EVA and EVA NEXUS for silicone oil extraction.

10. Micro Injection

In addition to the EVA the EVA NEXUS has a Micro Injection functionality, which is basically the same functionality as VFI, in a smaller and more precise volume dosing. The VFI function can be set in the range 0-6 bar, with step size 0,5 bar. The MI function can be set in the range 0-2 bar, with step size of 0,1 bar.

10. Endodiathermy.

Although the design is somewhat different, both EVA and EVA NEXUS use similar principles of operations to drive the diathermy handpiece to coagulate tissue

5.3 Patient safety with the EVA Nexus device

This field observation study will be performed to obtain more information on the safety and daily use of the EVA Nexus device in routine phaco/vitrectomy surgery. This information can lead to small adjustments to the device to further fine tune a safe device which can be used by other surgeons.

During a vitrectomy surgery, the surgeon removes the vitreous gel. This is done using a mini-guillotine of half millimeter diameter (or even less in 27G surgery) that is inserted in the eye. Meanwhile, an infusion fluid is injected in the eye. Sufficient fluid irrigation is mandatory to avoid a drop in the eye pressure which can lead to retinal or choroidal hemorrhage. On the other hand, it must be avoided to have the eye pressure elevate too high, since this can block the arterial blood supply which can lead to permanent damage of the eyesight of the patient.

The EVA Nexus device has an automated system, which allows better control of the eye pressure during the surgery compared to existing vitrectomy technology.

Another novel feature on this device is the improvement of the guillotine itself. The faster the guillotine can go backwards and forwards, the safer the surgery can be performed. The EVA Nexus device can keep up to a speed of 20000 cuts per minute, whereas in even the most performant devices the speed is limited to 16000 cuts per minute.

Often vitrectomy is combined with lens surgery. The removal of the lens is nowadays done using a device that emulsifies the lens with ultrasonic waves. This technique is called "phaco-emulsification", which has been the golden standard in cataract surgery for more than 20 years. The hand-held phaco-emulsification probe connected to the EVA Nexus is the same probe as used on our present DORC EVA device, but the internal steering is redesigned to allow better fine-tuning of the surgical settings according to the preferences of the surgeon.

Besides the EVA Nexus itself, several of the disposable supplies of this surgical platform were optimized:

- Newly designed phaco needles improve anterior chamber stability during cataract surgery.
- The instrument cannulas used during vitrectomy were redesigned. The smaller outside part occupies less space hence will allow more movement of the eye during the surgery.
- The infusion line can connect to the infusion canula without the need to remove its sealing cap. This reduces the amount of surgical movements and allows better surgical flexibility when the infusion needs to be switched to another instrument cannula during surgery.
- The infusion line locks onto the infusion canula, reducing the incidence of a commonly occurring issue that the infusion line disconnects from the cannula during the surgery.

After brought under anesthesia, the patients is draped while the vitrectomy device is being prepared. This involves connecting of all the surgical supplies (see above) and priming of the device. This whole procedure takes 10-20 minutes, depending on the complexity of

the case. The packaging of the surgical supplies was reworked (reduction in the amount of packaging materials) and the infusion giving set has been simplified significantly for the EVA Nexus platform. This should shorten the total surgical time.

Surgical issues and/or (S)AE's that are related to the surgical device will always be observed either during the surgery or during the postoperative visit on day one. Late-onset complications such as proliferative vitreoretinopathy, retinal detachment etc. are considered non-related to the surgical device. Hence, in this study, data acquisition is terminated after the postoperative visit on day one, although the patient will have further postoperative follow-up according the standard of care.

6. OBJECTIVES

The primary objective and primary parameters are shown in the table below:

The main purpose of this study is to evaluate the intra-operative safety of a new surgical device.
	
Therefore, having no idea of the percentage of patients having complications, we make the hypothesis that minimum 5% of the patients will have complications. In order to make sure that we have at least 10 patients with complications, we plan recruit 250 patients in total in order to get at least 10 complications with EVA Nexus.
 
For this purpose, typical surgical parameters will be recorded during vitrectomy surgery:
 
 • Surgical indication • If combined phaco-surgery is performed: amount of phaco power used • Staining dyes (if used) • Amount of laser coagulates (if used) • Type of tamponade left in the eye: BSS+ liquid, air bubble, air, gas (type + concentration) or silicone oil (type) 
Specific adverse events that may occur during (phaco)vitrectomy will be recorded to assess the surgical safety ¹⁵⁻¹⁸: see list in Appendix A. This AE reporting is already present in the surgical report (KWS-Formasa) used for daily vitrectomy surgery using the DORC EVA device. The occurrence of these AE's during surgeries using the EVA Nexus will be compared to historical data retrieved from surgeries using the DORC EVA platform.
 
Device issues that caused some hindering during the surgery but that do not lead to an (S)AE, such as error messages/warnings that did occur, malfunctioning of supplies that required replacement etc. will be recorded.
 
See Appendix B for a full list, which is already part of our present surgical report (KWS-Formasa). The occurrence of these issues during surgeries using the EVA Nexus will be compared to historical data retrieved from surgeries using the DORC EVA platform.

---	---

The secondary objective and secondary parameters are shown in the table below:

Secondary objective	Secondary parameters
To evaluate the possible reduction of total surgical time.	The time that was required to prepare the EVA Nexus will be recorded (connecting of supplies + priming). During the study period, this time will also be recorded during surgeries performed with the DORC EVA device for comparison.
To evaluate possible (S)AE that may be related to the use of the surgical platform.	Rarely, adverse events that are related to the surgery may only become visible the day after the surgery. A typical example is a choroidal hemorrhage, which is related to variations in intraocular pressure during the surgery. Hence, standard as in the standard-of care, a postoperative check of the eye at the day after the surgery will be performed to determine the presence of such AE's.
To evaluate the impact of usage of the EVA NEXUS on the surgical parameters used during the procedure	
The surgical parameters include a range of data collected on the following:
 
Aspiration Irrigation / Infusion BSS Usage Vitrectomy Ultrasound Illumination Diathermy Micro-injection Silicone oil injection / extraction Laser

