7. CLINICAL INVESTIGATION DESIGN

7.1 Trial Design

Investigator-initiated, academic, mono-center, prospective, field observation study using a novel CE-labeled surgical platform.

The study will be terminated after a time period of three months. A maximum of 250 patients will be enrolled. The study will consist of 3 patient visits. Study follow-up is 1 day after the date of the vitrectomy surgery.

During surgery, intra-operative complications and issues will be recorded for safety assessment: see list in previous paragraph.

Typical postoperative follow-up after vitrectomy includes the clinical tests to assess that normal postoperative outcome is present, without the presence of adverse events.

Hence, the same clinical data will be collected in the study patients as in patients undergoing the standard-of-care.

This field observation study is conducted to obtain information about the complication rate of the EVA Nexus system which will be compared with the incidence of these complications occurring in surgeries performed using our present DORC EVA platform. ¹⁵⁻¹⁸

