8. CLINICAL INVESTIGATION POPULATION

8.1. Number of participants – sample size analysis

With a complication rate ranging from 5% up to 30% in previous studies, we have no a priori about the complication rate of the EVA Nexus system. We therefore consider a rather conservative hypothesis and expect to have around 5% of complications with the EVA Nexus system. We plan recruit 250 patients in total in order to get at least 10 complications with EVA Nexus. The estimated enrolment time is 6 months.

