13.2. The number of participants

Maximum 250, inclusion time 4 months.

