13.3. The level of statistical significance

For all analyses, the level of significance will be 5% two-sided significant level.

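### The sample-size rationale treats 10 patients with complications as assured by enrolling 250; at the plan's 5% rate the probability is 81%

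*Combined protocol and SAP*

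**What the plan says.** The sample size is argued in two places.

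- Section 6 (Objectives, primary objective table) says that the complication rate is unknown and then sets a lower bound: "we make the hypothesis that minimum 5% of the patients will have complications". It goes on: "In order to make sure that we have at least 10 patients with complications, we plan recruit 250 patients in total". The end of that sentence restates the target as 10 complications, without the word patients.
- Section 8.1 (Number of participants – sample size analysis) cites earlier experience, "With a complication rate ranging from 5% up to 30% in previous studies", calls its choice conservative, and says that the investigators "expect to have around 5% of complications with the EVA Nexus system". It concludes: "We plan recruit 250 patients in total in order to get at least 10 complications with EVA Nexus".

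Elsewhere 250 is an upper limit. The summary in section 4 says up to 250, section 7.1 says "A maximum of 250 patients will be enrolled", and section 13.2 says "Maximum 250, inclusion time 4 months".

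No section gives an assurance level, power, target precision or allowance for loss. The number is not linked to the primary analysis, which is a one-sample proportion test against 30%, 15% and 5% (sections 13.1 and 13.13.2).

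**The concern.** Section 6 presents a minimum count as secured by the sample size. What 250 patients at 5% deliver is an expected count of 12.5, and the observed count varies around it. A target of 10 lies only 2.5 patients below that expectation, so a shortfall is an ordinary outcome.

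This sentence, with its repetition in section 8.1, is the whole rationale for the sample size. The number of patients with complications also sets how much information the later analyses hold. Sections 13.1 and 13.13.3 compare patients with and without complications and then fit a regression with backward selection on that outcome. An ethics committee or a reader is entitled to know how likely it is that the planned number of such patients will be seen.

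**Working it through.** **Inputs.** Rate p = 5% (a minimum in section 6, around 5% in section 8.1). Target: at least 10 patients with complications (section 6). N = 250 (sections 6 and 8.1), a maximum in sections 4, 7.1 and 13.2. Patients are taken as independent, each counted once, with no loss.

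**Can 250 be reproduced?** Not uniquely, because no assurance level is stated.

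- Expected count only: 10 / 0.05 = 200, which is not 250.
- The same with an assumed 20% loss: 200 / (1 − 0.20) = 250. The documents give no loss figure.
- Smallest N with P(X ≥ 10) of at least 80% at p = 5%: 249 (probability 80.2%). This is practically the planned number, but the documents never state 80%.
- Smallest N for 90%, 95% and 99%: 282, 311 and 371.

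**Probability of reaching the target.** With X ~ Binomial(250, 0.05):

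- E(X) = 250 × 0.05 = 12.5
- P(X ≥ 10) = 1 − Σ(k = 0 to 9) C(250, k) × 0.05^k × 0.95^(250 − k) = 0.8054
- P(X ≤ 9) = 1 − 0.8054 = 0.1946, about one in five

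A Poisson approximation gives 79.9%, and a normal approximation with continuity correction gives 80.8%, so the result does not depend on the method.

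**By true rate, N = 250:**

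| True rate | Expected count | P(X ≥ 10) |
|---|---|---|
| 4% | 10.0 | 54.5% |
| 5% | 12.5 | 80.5% |
| 6% | 15.0 | 93.6% |
| 7% | 17.5 | 98.3% |
| 10% | 25.0 | 99.99% |

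The probability reaches 95% at a rate of about 6.2%.

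**By enrolment, p = 5%.** These numbers are illustrations, since the documents forecast no shortfall:

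| N | Expected count | P(X ≥ 10) |
|---|---|---|
| 250 | 12.5 | 80.5% |
| 240 | 12.0 | 76.4% |
| 225 | 11.25 | 69.2% |
| 200 | 10.0 | 54.5% |

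**Precision.** An observed 12/250 = 4.8% has an exact 95% confidence interval of 2.5% to 8.2%.

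**The case against.** The strongest reply is that section 6 calls 5% a minimum and section 8.1 reports earlier rates up to 30%. On that reading 81% is a floor, and at 7% or more the target is almost certain. This stands as a qualification, so rates on both sides of 5% have to be shown. It does not rescue the claim, because an assurance based on a minimum has to hold at that minimum. Section 8.1, with its rate of around 5%, does not exclude lower values either.

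Second, 250 sits next to the size for 80% assurance, so it may have been chosen deliberately. That also stands. A reader might infer that 250 is a miscalculation or too small, and the documents do not support this. What is missing is the assurance level.

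Third, the unit is ambiguous. Section 6 uses both patients with complications and complications, while section 8.1 uses only the latter. Appendix A lists complications as separate tick boxes, so one patient can contribute several. If events are counted, the chance of 10 at a 5% patient rate is above 81%. The calculation here applies to patients, the unit in the sentence that claims assurance.

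Fourth, no stopping rule, success criterion or analysis depends on reaching 10, and the primary test can be run with fewer. This is correct and limits the consequence.

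Finally, planning to recruit 250 and capping enrolment at 250 are compatible. A reader might infer from the cap, or from the differing enrolment periods in sections 7.1, 8.1 and 13.2, that fewer will be enrolled. The documents forecast no lower number. The cap shows only that 81% cannot be exceeded at 5%.

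**Conclusion.** The point holds as a misstatement of certainty. At the plan's own 5%, full enrolment of 250 gives an 80.5% chance of at least 10 patients with complications and a 19.5% chance of fewer. Under section 6 that is the lowest value the hypothesis allows; under section 8.1 it is the central value, falling to 54.5% at 4% and rising to 93.6% at 6%. At 5% it is also the best case, because enrolment cannot go above 250.

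The result assumes independent patients, one count per patient, and no loss through refused consent or missing data.

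A reader might go further and infer that the sponsor hopes for a rate below 5%, so that a shortfall is the likely outcome. The documents do not support this: section 8.1 says that there is no prior view of the rate, and section 6 treats 5% as a lower bound. The defect is confined to the claimed assurance and the unstated probability behind it.

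**What to change.** In sections 6 and 8.1, remove the wording that presents the target as assured, use one unit throughout (patients with at least one complication), and state:

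> With 250 patients and a 5% complication rate we expect 12.5 patients with complications; the probability of at least 10 is 81% (54% at 4%, 94% at 6%, 98% at 7%). An observed 12/250 would have an exact 95% CI of about 2.5% to 8.2%.

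If 80% assurance was the intended basis for 250, say so in the same place.

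The cost is a few sentences of protocol text, handled as an amendment under section 15.1. Enrolment, conduct and analyses do not change. The drawback is that the stated figure looks less favourable than the present claim.
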